8.2 Assessing Severity of Adverse Events

The severity of adverse events will be designated as mild, moderate, severe, life threatening, or fatal per NCI CTCAE version 4.0. If not specifically addressed in NCI CTCAE version 4.0, use the table below:

Mild – Grade 1	Transient or mild discomfort; requiring no limitation of activity; no therapy
Moderate – Grade 2	Mild-moderate impact on activity; requiring some assistance and medical intervention
Severe – Grade 3	Marked impact on activity; requiring some assistance and medical intervention
Life Threatening – Grade 4	Complete disability; requiring significant assistance and medical intervention and/or hospitalization
Death – Grade 5	Adverse event with fatal outcome

Table 2 Adverse Event Severity

This document contains confidential information. It is intended solely for the use of the principal investigator, co-investigators, staff, appropriate institutional review boards or ethical committees, and other required regulatory bodies.

The term "severe" is often used to describe the intensity (severity) of a specific event (as in mild, moderate, or severe myocardial infarction); the event itself, however, may be of relative minor medical significance (such as severe headache). This is not the same as "serious", which is based on subject/event outcome or action criteria usually associated with events that pose a threat to a subject's life or functioning. Seriousness (not severity) serves as a guide for defining regulatory reporting obligations.

8.3 Assessing Relationship to Study Treatment

All AEs will be categorized by the Investigator with respect to their possible relationship to the IMP. The relationship of the AE to study treatment will be assessed by the investigator to be not related, unlikely, possible, probable or definite, as follows:

- Not related: No relationship between the AE and the administration of IMP, judged clearly and incontrovertibly due to extraneous causes (disease, environment etc.).
- Unlikely: The AE is more likely due to an alternative explanation such as concomitant medication(s), concomitant disease(s) and/or the time relationship suggests that a causal relationship is unlikely.
- Possible: The AE might be due to the administration of IMP. An alternative explanation such as concomitant medication(s), concomitant disease(s) is inconclusive. The time relationship is reasonable therefore the causal relationship cannot be excluded.
- Probable: The AE might be due to the administration of IMP. An alternative explanation such as concomitant medication(s), concomitant disease(s) is less likely. The time relationship is suggestive, i.e. it is confirmed by de-challenge.
- Definite: There is no uncertainty in relationship to the administration of IMP. The AE cannot be reasonably explained by an alternative explanation such as concomitant medication(s), concomitant disease(s). The time relationship is very suggestive, i.e. it is confirmed by de-challenge and re-challenge.

"Not related and Unlikely related" correspond to "no reasonable possibility". "Possible, probable and definite" correspond to "reasonable possibility".

8.4 Recording of Adverse Events

All AEs encountered during the clinical study will be recorded in detail in the source documents and documented in the eCRF, from signature of the ICF through the end of the short term follow-up phase. All AEs that meet the seriousness criteria (Section 8.6) should

This document contains confidential information. It is intended solely for the use of the principal investigator, co-investigators, staff, appropriate institutional review boards or ethical committees, and other required regulatory bodies.

also be recorded on the SAE Report Form. All SAEs must be reported to the sponsor or delegated organization within the timeline stated in Section 8.7.

The recording of AEs will be based on data obtained from the following sources:

- Medical and surgical history
- Physical examinations including vital signs
- Clinical laboratory test results
- Subject diary

All clinical events, including both observed (such as any reaction at sites of application) and volunteered problems, complaints, or symptoms, are to be recorded. The need to capture this information is not dependent upon whether the clinical event is associated with the use of any IMP.

Clinical symptoms or events such as mucositis or stomatitis are not to be recorded as an AE or SAE.

Clinically significant bacteremia and clinical sepsis should be recorded as AE or SAE.

The potential adverse event profile of the IMP regimen is located in Appendix H.

If at anytime during the study a subject develops symptoms suggesting clinically significant bacteremia that can be attributed to sAGX0085 (as determined by three consecutive positive blood cultures), study treatment will be discontinued.

In the event that a subject develops symptoms suggesting clinically significant bacteremia or sepsis, the subject should be treated per the site's standard of care. Prior to treatment of the event, 3 consecutive whole blood samples need to be taken from the subject and aliquots of these samples must be sent immediately to Intrexon Actobiotics for analysis. The first two samples are to be drawn together and the third sample is to be drawn 10-15 minutes after the first tube is drawn. Detailed information can be found in the laboratory manual.

A disposition plan for the management of clinical sepsis is provided in appendix I.

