6.5 Health and Economic Outcomes

- Insertion of, or need for use of, gastrostomy tube feedings will be assessed and recorded (US sites only)
- Unplanned office visits, ER visits, or hospitalizations will be assessed and recorded (US sites only)

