8.6 Serious Adverse Event Definition

In addition to classifying the AE as mild, moderate, severe, life-threatening or fatal, the Investigator should determine whether or not an AE is an SAE. The Investigator shall make an accurate and adequate report on any SAE to the Sponsor or its designee and to any IRB/IEC that has reviewed and is continuing to review the study regarding any SAEs (see Section 8.10).

An SAE is defined as any AE occurring at any dose regardless of relationship to IMP that results in any of the following outcomes:

- Death
- A life-threatening adverse drug event (does not include a reaction that, had it occurred in a more severe form, might have caused death)
- Inpatient hospitalization or prolongation of existing hospitalization
- Persistent or significant disability or incapacity
- Congenital anomaly or birth defect in the offspring of a subject who received IMP
- Other significant medical events

Important medical events that may not result in death, be life-threatening or require hospitalization may be considered an SAE when, based upon appropriate medical judgment, they may jeopardize the subject and may require medical or surgical intervention to prevent one of the outcomes listed above.

Complications that occur during hospitalization are AEs. If a complication prolongs hospitalization, the event causing the prolongation is an SAE. Planned hospitalizations are not considered SAEs.

"Inpatient hospitalization" means the subject has been formally admitted to a hospital for medical reasons. This may or may not be overnight. It does not include presentation at an emergency department.

In instances where an SAE occurs in a subject receiving a product not licensed by the Sponsor as a control or concomitant drug, the SAE must be processed and reported as if it were a product of the Sponsor.

This document contains confidential information. It is intended solely for the use of the principal investigator, co-investigators, staff, appropriate institutional review boards or ethical committees, and other required regulatory bodies.

Unexpected AEs are further defined as any adverse experience where the specificity or severity of which is not consistent with the applicable product information (i.e., current Investigator Brochure).

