11.4 Data Safety Monitoring Board

An independent DSMB will be constituted before the start of the study. The DSMB will supervise the ethical performance of the study and review safety data arising during the study according to the procedures described in the DSMB Charter. The Charter will describe the following activities:

- Committee membership
- Committee responsibilities
- Frequency and content of meetings
- Procedures for the review and assessment of the safety data of the first 10 subjects on AG013 having completed study treatment
- Procedures for the expedited review for clinically significant bacteremia and clinical sepsis
- Procedures for the review and assessment of the cumulative safety data
- Criteria for determining whether to recommend stopping the study for unacceptable harm.

The DSMB will be composed of 3 or more members who will have relevant experience in the treatment of subjects with OM and/or HNC and the conduct of randomized clinical trials. One member will be a biostatistician experienced in phase 2 and 3 oncology clinical trials, and none of the members will be Investigators in this study or employees of the sponsor . Any AE that leads to a subject's treatment termination, and any SAE a subject experiences during the study, will be regularly reported to the DSMB, as specified in the Charter. The DSMB will receive unblinded data for any subject in the case of these safety events.

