Appendix H: Potential Adverse Event Profile of the IMP Regimen

Relative to the risk of clinical sepsis due to the study organism, the study organism is nonpathogenic, preclinical safety studies failed to show any evidence for clinical sepsis even after intravenous administration of the study organism in severely neutropenic animals, and subjects in other clinical trials of a similar mucosally administered non-pathogenic organism have not demonstrated bacteremia or sepsis. No patients of the phase 1b study AG013-ODOM-101 (a group that was myelosuppressed) developed sepsis from AG013 nor could AG013 be detected in the blood. No deaths or discontinuations due to AEs occurred in this study.

The chances of AG013 adversely affecting the course of oral mucositis seem equally remote. Preclinical studies have shown a clear beneficial effect on severity and duration of oral mucositis in a relevant animal model. In addition, results of a clinical study in which another form of topically administered trefoil factor was tested demonstrated its benefit in modulating the course and severity of oral mucositis. Several efficacy endpoints were measured as exploratory endpoints in the phase 1b AG013-ODOM-101 study. Subjects who received AG013 had a lower percentage of days with ulcerative mucositis, and more subjects who received AG013 on any dosing schedule had no or only 1 day of ulcerative mucositis compared to subjects who received placebo.

Within the intended study population, there is no particular population at risk, and the risks are not predictable or preventable.

Clinical sepsis due to the study organism is reversible and time-limited when antibiotic therapy is applied. Worsening of mucositis is reversible and time-limited.

Following adverse events linked to the IMP regimen can potentially occur:

- Clinically significant bacteremia
- Clinical sepsis

This document contains confidential information. It is intended solely for the use of the principal investigator, co-investigators, staff, appropriate institutional review boards or ethical committees, and other required regulatory bodies.

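### Section 8.4 bars mucositis and stomatitis from AE and SAE recording without exception, so a serious, treatment-ending or rinse-related case does not enter the event reports sent to the DSMB

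*Protocol*

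**What the plan says.** Protocol Section 8.4 sets a broad recording rule: "All clinical events, including both observed (such as any reaction at sites of application) and volunteered problems, complaints, or symptoms, are to be recorded". It adds that the duty does not depend on a link to the IMP. It then says: "Clinical symptoms or events such as mucositis or stomatitis are not to be recorded as an AE or SAE". The next sentence confirms that bacteremia and sepsis are recordable. Nothing comparable is said for mucositis that is serious or attributed to the product.

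Section 8.6 begins: "An SAE is defined as any AE occurring at any dose regardless of relationship to IMP that results in any of the following outcomes". Section 11.4, repeated in SAP 4.3, describes the event stream to the board: "Any AE that leads to a subject's treatment termination, and any SAE a subject experiences during the study, will be regularly reported to the DSMB". Section 11.4 leaves to the DSMB Charter the content of meetings, the review of the first 10 subjects on AG013, the criteria for stopping for harm, and "Procedures for the review and assessment of the cumulative safety data".

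Appendix H says: "The chances of AG013 adversely affecting the course of oral mucositis seem equally remote". It adds that any worsening would resolve with time. Its closing list of possible IMP-linked events names only bacteremia and sepsis.

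Mucositis is measured separately. Section 6.3.1 has blinded, trained evaluators record the WHO grade twice weekly in the active phase and weekly in short term follow-up.

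**The concern.** Keeping an expected efficacy outcome out of AE reporting is reasonable. The difficulty is that this exemption has no limit, and it covers inflammation of the very tissue to which the product is applied. A site that sees an inflamed mucosa and suspects the rinse has one sentence telling it to record the reaction and another telling it not to record stomatitis as an AE.

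If the site follows the second sentence exactly, a hospital admission for mucositis produces no SAE form. Stopping the IMP because of mucositis produces no AE leading to discontinuation. A reaction blamed on the rinse produces no related AE. Safety and tolerability form a primary objective (Section 2), and recruitment continues after the first-10 review if no safety signals are found (Section 3). The tolerability ratings cover taste, consistency and smell (Section 10.6), so they do not fill the gap.

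**Working it through.** The plan gives no figure to reproduce on this point. The check is a trace through the text.

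1. **Is the ban conditional?** No. The sentence in Section 8.4 covers both AE and SAE and does not mention seriousness, relatedness or stopping IMP.

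2. **Can a serious case enter through Section 8.6?** No. Seriousness there is a property of an AE. An event that may not be recorded as an AE cannot qualify, even when it leads to an outcome on the list, such as inpatient admission.

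3. **Are serious cases plausible on the protocol's own account?** Yes. Section 1.1.2 links even mild mucositis to more frequent hospitalization in head and neck cancer. Appendix B defines grade 4 by the need for IV or tube feeding.

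4. **Which safety mechanisms depend on AE or SAE status?**
   - event reports to the DSMB (Section 11.4, SAP 4.3);
   - reports of unexpected, related SAEs to regulators (Sections 8.7 and 8.10);
   - the medical monitor's unblinded assessment of repeated SAEs attributed to IMP, with a possible accrual hold (Section 10.10);
   - TEAE, SAE and discontinuation summaries and listings (Section 10.6, SAP 8.8.2).

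   Neither Section 10.6 nor SAP 8.8 lists the WHO grade as a safety measure.

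5. **Where else would worsening be seen, and when?** SAP 8.7.1 tabulates WHO grades by visit and arm, and the primary test is two-sided, so harm could show there. SAP 8.4 tabulates reasons for study withdrawal. But unblinding for analysis follows the last subject's short term follow-up (Section 9), and no interim analysis is planned (Section 10.8). Neither document states a route by which grades by arm reach the DSMB during the trial.

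6. **Is hospitalization captured separately?** The documents disagree. Sections 6.5 and 10.1.7 limit it to US sites. Sections 7.3.3 to 7.3.5 and the Appendix D schedule require it with no regional limit.

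**The case against.** The best case for the plan is that mucositis is the primary endpoint and is graded by trained, blinded observers far more carefully than AE forms would manage. Duplicate AE records would add noise. For non-serious mucositis this stands, and the exemption should remain.

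The two sentences in Section 8.4 can also be read together, as a general rule with a specific carve-out. Burning, allergic reaction, bleeding and infection are not named in the ban, and sequelae such as dehydration are not expressly excluded. That reading is fair, and it makes the wording ambiguous rather than impossible to follow. It does not supply an exception, because stomatitis is named outright.

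A reader might infer that the DSMB will clear its first-10 and cumulative reviews without seeing any mucositis data. The documents do not support that. The sentence in Section 11.4 describes event reports, not the whole board package, and the Charter could include WHO grades. What stands is that neither the protocol nor the SAP says so.

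There is also a blinding cost. Under Section 11.4 the DSMB receives unblinded data on subjects with SAEs, and under Section 10.10 the medical monitor may assess repeated IMP-attributed SAEs unblinded. Some primary-endpoint events would now pass through those channels. This argues for narrow exceptions rather than none.

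Finally, Appendix H calls the risk remote. That bears on how likely the harm is, not on whether a case would be reported if it occurred.

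**Conclusion.** The point holds and should be corrected. Followed literally, Section 8.4 keeps reportable events out of the SAE reports, the discontinuation tables and the DSMB's event reports. This rests on two assumptions: that sites apply the sentence as written, and that the Charter does not already supply WHO grades by arm. If the Charter does, the DSMB part shrinks to stating so in the protocol; the missing SAE and discontinuation records remain.

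The size cannot be calculated. The documents give no rate for mucositis that is serious, ends IMP treatment or is attributed to the rinse. A reader might take the Section 10.2 incidences as the measure: 0.75 × 80 + 0.50 × 80 = 60 + 40 = 100 of 160 evaluable subjects, or 5 to 7.5 of the first 10 on AG013. Those figures count all expected severe mucositis, most of which may be the ordinary effect of chemoradiation, and Section 8.2 itself separates severe from serious. Nor could severe-mucositis incidence in the first 10 show much: at a 75% background, all 10 being severe has probability 0.75^10 = 0.056.

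A reader might also conclude that mucositis-related admissions in Europe go unrecorded altogether. The visit procedures contradict the US-only limit, so this is an inconsistency to reconcile, not an established gap. Nor would harm stay hidden at the end of the trial, since the by-arm grade tables and the two-sided test remain.

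**What to change.** - **Section 8.4.** Keep the exemption for non-serious mucositis captured by WHO grade. Require an AE or SAE record when mucositis or stomatitis meets a Section 8.6 seriousness criterion, is the reason IMP is stopped, or is judged related to IMP under Section 8.3. Reconcile the ban with the application-site sentence.
- **Section 11.4 and SAP 4.3.** State that the independent DSMB receives WHO-grade distributions by arm in its closed safety reports, for harm review only. This complements the individual reports, because attributing one case to the rinse is hard against a high background rate.
- **Sections 6.5 and 10.1.7.** Reconcile the US-only limit on hospitalization with the unrestricted recording in Sections 7.3.3 to 7.3.5 and Appendix D.

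The cost is some additional AE and SAE forms, one table from data already collected, and some primary-scale data seen by the unblinded DSMB. Neither document contains an efficacy stopping rule, so a harm-only review spends no alpha. The protocol should also say how the medical monitor's unblinded assessment in Section 10.10 applies to these events, so that knowledge of allocation on the primary endpoint stays contained.

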8.5 Adverse Event Follow-up Period

All subjects with AEs will be followed until the event resolves, stabilizes, becomes chronic, the subject completes the study or the subject is lost to follow-up.

This document contains confidential information. It is intended solely for the use of the principal investigator, co-investigators, staff, appropriate institutional review boards or ethical committees, and other required regulatory bodies.

8.6 Serious Adverse Event Definition

In addition to classifying the AE as mild, moderate, severe, life-threatening or fatal, the Investigator should determine whether or not an AE is an SAE. The Investigator shall make an accurate and adequate report on any SAE to the Sponsor or its designee and to any IRB/IEC that has reviewed and is continuing to review the study regarding any SAEs (see Section 8.10).

An SAE is defined as any AE occurring at any dose regardless of relationship to IMP that results in any of the following outcomes:

- Death
- A life-threatening adverse drug event (does not include a reaction that, had it occurred in a more severe form, might have caused death)
- Inpatient hospitalization or prolongation of existing hospitalization
- Persistent or significant disability or incapacity
- Congenital anomaly or birth defect in the offspring of a subject who received IMP
- Other significant medical events

Important medical events that may not result in death, be life-threatening or require hospitalization may be considered an SAE when, based upon appropriate medical judgment, they may jeopardize the subject and may require medical or surgical intervention to prevent one of the outcomes listed above.

Complications that occur during hospitalization are AEs. If a complication prolongs hospitalization, the event causing the prolongation is an SAE. Planned hospitalizations are not considered SAEs.

"Inpatient hospitalization" means the subject has been formally admitted to a hospital for medical reasons. This may or may not be overnight. It does not include presentation at an emergency department.

In instances where an SAE occurs in a subject receiving a product not licensed by the Sponsor as a control or concomitant drug, the SAE must be processed and reported as if it were a product of the Sponsor.

This document contains confidential information. It is intended solely for the use of the principal investigator, co-investigators, staff, appropriate institutional review boards or ethical committees, and other required regulatory bodies.

Unexpected AEs are further defined as any adverse experience where the specificity or severity of which is not consistent with the applicable product information (i.e., current Investigator Brochure).

Pregnancy in a female study participant, occurring after signature of the ICF is considered immediately reportable event using specific reporting forms and must be reported within 24 hours after the investigator has gained knowledge of it. The subject will discontinue IMP and must be withdrawn from the study. Details of the outcome of the pregnancy (e.g. full term delivery, stillbirth, congenital anomaly, miscarriage) will be collected and reported no longer than one month after the expected due date. Any abnormal outcome in the neonate will be followed-up.

8.7 Reporting of Serious Adverse Events

The Sponsor is required to inform worldwide regulatory authorities of SAEs that meet specific criteria. Therefore, the Sponsor must be notified immediately regarding any SAE that occurs after informed consent is obtained. All SAEs and follow-up information must be reported within 24 hours after the investigator has gained knowledge of it, as required by local regulations, by faxing a completed SAE Report Form to the fax number below or emailing a completed SAE Report Form to the PSI Safety Desk at [contact].

Country	Toll-free Safety Line Numbers
Belgium	[name] [name] (Brussels) [name] (Antwerp)
Germany	[name]
US	[name] [name] [name]
ИК	[name]

Table 3: Toll-free Safety Line Numbers for SAE Reporting*

*Any fax sent to these lines will be routed to safety desk e-mail address ([contact])

This document contains confidential information. It is intended solely for the use of the principal investigator, co-investigators, staff, appropriate institutional review boards or ethical committees, and other required regulatory bodies.

The necessity and time requirements for reporting SAEs to the Sponsor or designee and regulatory agencies are as follows:

- All SAEs will be reported via the eCRF system within 24 hours of the investigator's first knowledge of the event, even if the event does not appear to be related to AG013. In case reporting via the eCRF is not available, the SAE may be reported via fax in order to meet the reporting requirements.
- Reports of any pregnancy in a subject, must also be reported on the Pregnancy Report Form within 24 hours of the investigator's first knowledge of the event (see section 8.6) and fax completed form to PSI Safety Desk or e-mail a scanned copy to [contact], even if no AE has occurred.
- For all SAEs, a detailed written description that includes anonymized copies of available relevant patient records, autopsy reports, and other documents will be sent within 24 hours of the investigator's first knowledge of the SAE.
- SAEs that are life threatening or result in death, and are unexpected and related to AG013 will be reported to regulatory authorities within 7 days of receipt of the event. Any follow up to the initial SAE report will be submitted to regulatory authorities within 8 days of the initial report (ie, within15 days of receipt of initial report).
- Any SAE that is unexpected and related to AG013, results in hospitalization or prolongs an existing hospitalization, results in persistent or significant disability/incapacity, or is a congenital anomaly/birth defect will be reported to regulatory authorities within 15 days of receipt of the report. Some regulatory authorities may have alternative timelines for submission of suspected unexpected serious adverse reactions. In those cases, specific local requirements for submission of SAE reports will be applied.
- All SAEs will be followed until resolution or stabilization. Follow-up reports for SAEs reported as 7- 15-day reports will be submitted within the same time frame as the initial report.

Additionally, the IRB and/or IEC must be notified in writing of any unexpected, related SAEs or as required by the local IRB/IEC. It is the responsibility of the investigator/contract research organization (CRO) to notify the IRB/IEC.

If applicable, SAEs will be reported to the appropriate regulatory agencies by the Sponsor or designee. In case the local regulations require notification through the investigator, the Sponsor will facilitate this process.

The information to be recorded for SAEs should include the following:

This document contains confidential information. It is intended solely for the use of the principal investigator, co-investigators, staff, appropriate institutional review boards or ethical committees, and other required regulatory bodies.

- The onset of any new AE or the worsening of an observation documented from signature of the ICF through the end of the short term follow-up phase
- The specific type of event in standard medical terminology
- The duration of the clinical event (start and stop dates)
- The severity of the clinical event
- Seriousness (SAE) criteria
- Relevant laboratory and examination results
- Dosing schedule of IMP
- Indications and dosing schedules of concomitant medications
- Relationship of the AE to the IMP as defined in Section 8.3
- Management of IMP administration and other action taken to alleviate the clinical events
- Past medical and surgical history and concurrent diseases
- De-challenge/re-challenge results, if applicable
- The outcome of the clinical event

